Chronic Kidney Disease (CKD) represents a significant global health issue that imposes a considerable burden on public health systems worldwide [1]. CKD is characterized by a gradual and irreversible decline in kidney function over time [2]. The disease progresses through five stages, eventually leading to End-Stage Renal Disease (ESRD) or kidney failure, where patients typically require dialysis or a kidney transplant to survive [3]. Due to the increasing prevalence of aging populations and potential risk factors such as diabetes and hypertension, the incidence of CKD is rising globally [4]. CKD ranks among the top ten causes of death worldwide [5]. The economic costs associated with CKD are substantial for both individuals and society as a whole [6], particularly for the treatment expenses of ESRD which might be prohibitively expensive in the form of dialysis or kidney transplantation [7]. Many healthcare systems in low- and middle-income countries struggle to cope with these costs [8]. As CKD progresses, affected individuals may experience a variety of complications, including cardiovascular disease, anemia, bone disease, and a decline in quality of life [9], often leading to additional healthcare needs and expenses [10]. This disease can profoundly affect patient's lives, impacting their work and daily activities [11]. Such realities may contribute to increased societal costs, including productivity losses and the need for caregiver support [12]. There are disparities in the incidence and treatment of CKD among different socioeconomic groups and regions, with vulnerable populations often experiencing higher rates of the disease and lacking access to adequate care and treatment options [13]. Efforts to prevent and treat CKD encounter various barriers, such as a lack of symptoms in the early stages leading to late diagnosis, and the complexities of managing the risk factors of the condition [14]. The global burden of CKD is immense, impacting health systems, economies, and the quality of life of patients [1]. There is a need for raised awareness, early intervention, and equitable treatment opportunities to address the challenges posed by this disease.

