Nevertheless, the effectiveness and tolerability of finerenone in patients with non-diabetic chronic kidney disease (CKD) have not yet been clearly established [25]. The design of this study aims to determine whether the renal protective benefits of finerenone also apply to non-diabetic CKD patients, including those with an estimated glomerular filtration rate (eGFR) below 15 ml/min/1.73m² [26]. To our knowledge, our investigation is pioneering in assessing the therapeutic potential and safety profile of finerenone for this specific patient group [27].

II. Research Objective

To assess the progression of kidney disease in non-diabetic CKD patients following the use of finerenone, and to analyze the safety profile of finerenone.

III. Research Content

Investigate the changes in renal function in non-diabetic CKD patients after the administration of finerenone.

Analyze the relationship between the use of finerenone and cardiovascular events.

Evaluate the safety of finerenone treatment.

IV. Research Methodology

(A) Study Design

This project is a single-center, retrospective cohort study.

(B) Study Population

The study population comprises patients who were hospitalized for treatment or followed up on an outpatient basis in the Department of Nephrology, the First Hospital affiliated with Harbin Medical University, starting from December 15, 2023. The baseline for the study is defined as the occasion when a patient with CKD (either as a primary or secondary diagnosis) was first admitted to the nephrology department for hospital treatment or an outpatient visit.

Inclusion criteria:

- (1) Patients who were hospitalized or followed up on an outpatient basis in the Department of Nephrology, the First Hospital affiliated with Harbin Medical University, starting from December 15, 2023;
- (2) Patients with non-diabetic kidney disease;
- (3) Patients with electronic medical records available.

Exclusion criteria:

- (1) Type 2 diabetes mellitus;

(2) Patients who refuse to participate.

(C) Study Variables

In accordance with the research objectives, the project will collect the following variables:

Baseline patient characteristics: including age, gender, stage of kidney disease, comorbidities, medication history, etc.

Use of finerenone: including dosage, duration of therapy, etc.

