Ensure that all data collection and processing adhere to the ethical guidelines of the hospital and research institution, local medical regulations, and data privacy laws. If direct communication

with patients is necessary to collect data, obtain informed consent from the patient.

V. Statistical Analysis

In a single-center retrospective study, the data analysis process is complex and multi-step, aimed at extracting meaningful conclusions and insights. Below is a detailed description of the data analysis:

Data cleaning:

Prior to formal analysis, data cleaning is conducted to remove incomplete, incorrect, or inconsistent records.

Missing data are appropriately addressed, for example through imputation or deletion of missing entries.

Duplicate records are checked and resolved to ensure the uniqueness of analysis.

Descriptive statistical analysis:

Descriptive statistical analysis is performed on basic patient characteristics, including age, gender, stage of CKD, etc.

Medication usage of finerenone is quantified (dose, duration of treatment, etc.).

Primary and secondary outcome measures are descriptively analyzed (e.g., changes in renal function, incidence of cardiovascular events).

Exploratory Data Analysis (EDA):

Data within the set is visualized using bar charts, box plots, scatter plots, and other visualization tools to explore potential patterns or trends.

Variables potentially affecting study outcomes are extracted for exploration of relationships between variables.

Hypothesis testing:

If the study aims to compare renal function before and after treatment with finerenone, hypothesis testing might be conducted using parametric or nonparametric methods such as paired sample t-tests or Wilcoxon signed-rank tests.

In the presence of multiple groups (e.g., patients with different stages of CKD), methods such as ANOVA or Kruskal-Wallis may be used to compare differences between groups.

Regression analysis:

Linear regression analysis is conducted to assess the degree of association between continuous variables.

Binary logistic regression analysis is utilized for non-continuous outcome variables, such as the occurrence of cardiovascular events.

Multivariate regression analysis may be applied, if appropriate, to adjust for potential confounding factors.

Survival analysis:

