If the study includes analysis of follow-up data, such as tracking the progression of CKD, Kaplan-Meier survival curves can be used for description, and Log-rank tests to assess differences between treatment and control groups.

Cox proportional hazards model could be employed to determine the relationship between

treatment and outcomes while adjusting for confounders.

Use of statistical software:

Complex statistical analyses are performed using statistical software packages such as SPSS, Stata, R, or Python.

Data integrity is maintained throughout the analysis, and all analysis steps are documented for later review.

Interpretation of results:

Attention is given to the levels of statistical significance, and methods like Bonferroni correction are applied to address issues of multiple comparisons.

Statistical findings are translated into clinically meaningful narratives that can be understood and used by physicians or researchers.

Discussion and comparison:

Results are compared with existing literature and other studies to discuss possible reasons for any discrepancies.

Limitations of the study findings are highlighted, and areas needing further research are proposed.

Report writing:

Based on the results of the analysis, a research report or scientific paper is composed, including the methods, data analysis process, results, conclusions, and recommendations.

Through these steps, researchers can effectively draw conclusions from large data sets and provide evidence for clinical decision-making or further research. Throughout all these stages, adherence to statistical principles, data privacy regulations, and ethical guidelines is crucial.

VI. Ethics

Ethical Committee Review

The research protocol, informed consent forms, and any materials directly related to the patients must be submitted to the ethics committee for written approval before the research can formally commence. The ethics committee must be notified in writing upon cessation and/or completion of the study. Researchers are required to promptly report any changes occurring in the research work to the ethics committee (such as revisions to the research protocol and/or informed consent forms) and must not implement these changes prior to obtaining the committee's approval, unless the changes are made to eliminate apparent and direct risks to the enrolled patients.

Informed Consent

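### The before/after renal test ignores the time between the two values, and no follow-up time, minimum duration or cut-off is set, so it does not estimate progression

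*Combined protocol and SAP*

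**What the plan says.** Section II gives the aim as "To assess the progression of kidney disease in non-diabetic CKD patients following the use of finerenone". The introductory background describes the disease in these terms: "CKD is characterized by a gradual and irreversible decline in kidney function over time".

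Section V, under Hypothesis testing, covers the before/after question: "If the study aims to compare renal function before and after treatment with finerenone, hypothesis testing might be conducted using parametric or nonparametric methods". The examples that follow are the paired t-test and the Wilcoxon signed-rank test. No time is given for the later measurement.

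Section IV (B) admits patients "starting from December 15, 2023" and gives no end date. Its three inclusion criteria concern site and date, non-diabetic kidney disease, and "Patients with electronic medical records available". None sets a minimum time on treatment or under observation. The same section fixes the starting point: "The baseline for the study is defined as the occasion when a patient with CKD (either as a primary or secondary diagnosis) was first admitted". An outpatient visit also counts. Baseline is thus first contact with nephrology, not the start of the drug.

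Section IV (C) collects "Use of finerenone: including dosage, duration of therapy, etc". Section V summarises dose and duration descriptively but does not carry duration into the paired test. Under Survival analysis the plan adds: "If the study includes analysis of follow-up data, such as tracking the progression of CKD, Kaplan-Meier survival curves can be used for description". Log-rank and Cox methods are also offered there, all as options.

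**The concern.** Progression is change per unit of time. A paired test on two values per patient estimates the mean change over whatever intervals the patients happen to have. If those intervals are unequal and unplanned, the mean change cannot be read as a rate, and the size and significance of the result depend partly on how long patients were observed.

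Two things are at stake. First, in a slowly declining disease, a short interval gives a small expected change, and a non-significant paired test is then likely even if the drug does nothing. The plan has no margin or definition of stability to guard against reading that as preserved function. Second, because baseline is first nephrology contact, the interval can include time before finerenone, so part of the measured change may not relate to treatment at all.

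This is separate from the question of a control group. With controls added, unequal intervals in users and non-users would still distort a comparison of raw changes.

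**Working it through.** The documents state no planned sample size, alpha, power, effect size or SD, so there is no figure of the plan's own to reproduce. The numbers below are illustrations.

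**Inputs**
- From the documents: n = 43, the cases already organised (section VIII). This is not a planned sample size.
- Assumed: two-sided 0.05; linear eGFR decline of 2 to 5 ml/min/1.73m2 per year, unaltered by treatment; SD of within-patient change 5 to 10, constant over time; the same interval for every patient.

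**Step 1: what the mean change measures.** Under linear decline, expected loss = annual rate × months / 12.
- A rate of 4 per year seen over 6 months gives 4 × 6/12 = 2.0. A rate of 2 per year seen over 12 months gives 2 × 12/12 = 2.0. A two-fold difference in progression gives the same paired change.
- If users and non-users both decline at 4 per year, but users are seen for 6 months and non-users for 12, the losses are 2.0 and 4.0. That is a difference of 2.0 with no drug effect.

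**Step 2: probability that the paired t-test detects an unaltered decline.** The non-centrality parameter is expected loss / (SD / √43). Power is the probability that a noncentral t with 42 degrees of freedom falls outside ±2.018.

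Worked case: 3 per year, SD 8, 3 months. Expected loss 3 × 3/12 = 0.75; standard error 8/√43 = 1.22; non-centrality 0.75/1.22 = 0.615; power 9%.

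| Decline per year, SD | 3 months | 6 months | 12 months |
|---|---|---|---|
| 2, SD 10 (least favourable) | 6% | 10% | 25% |
| 3, SD 8 | 9% | 22% | 67% |
| 4, SD 6 | 19% | 57% | 99% |
| 5, SD 5 (most favourable) | 36% | 89% | over 99% |

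At 3 months, a wholly ineffective drug would therefore give a non-significant test in 64% (100 − 36) to 94% (100 − 6) of such studies.

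**Step 3: what a confidence interval would show.** In the worked case the 95% half-width is 2.018 × 1.22 = 2.46. Around the expected change of −0.75 the interval runs from −3.21 to +1.71 over 3 months. Multiplied by 4, that is about −12.8 to +6.8 per year, which is compatible with rapid loss as well as with none.

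**The case against.** The paired test is worded conditionally and is not the only route to progression. The survival methods accommodate unequal follow-up, section IV (C) lists renal function decline among the kidney events, and section V allows regression adjustment. This stands in part: it would be wrong to treat the paired test as the plan's sole analysis. But the survival methods are optional, have no stated time origin or censoring rule, and analyse events rather than continuous eGFR. The linear regression names no outcome, time variable or repeated-measures structure. None of them fixes the interval for the before/after comparison.

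Section VIII reports significant differences in the 43 organised cases, so the one empirical remark in the documents is not a null result. That is fair, but variable, direction and timing are not given, so the remark neither supports nor refutes the point.

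Some stronger readings are tempting and should be resisted:
- A reader might infer that the interval mix decides the sign of the result, or that the drug is irrelevant to it. Under constant decline the expected change is a loss at every interval; only its size and significance vary. A drug that alters the slope alters the change at any given interval.
- A reader might infer that the investigators will report non-significance as stability. The documents do not say so, and section V undertakes to highlight limitations. The supportable statement is that the plan does not prevent this reading.
- A reader might infer that the cohort consists mostly of recent starters. No distribution of start dates is given.

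**Conclusion.** The point holds. The objective is a rate, the only methods named for before/after renal function ignore time, and neither a follow-up window, a minimum duration nor a cut-off is set. Baseline is also not tied to the start of finerenone. Run as written on unequal intervals, the paired test does not estimate progression.

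The size of the risk is uncertain. Across the assumed slopes and SDs, detection of an unaltered decline is 6 to 36% at 3 months, 10 to 89% at 6 months and 25% to over 99% at 12 months. These ranges rest on n = 43, linear decline, constant SD and equal intervals, none of which the documents establish for the final study. Power near 99% at 12 months is a favourable case, so a 12-month rule would not by itself guarantee an informative test. The change should be made before the final analysis, because otherwise the choice of later value stays open once the data are known.

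**What to change.** Make the continuous renal outcome the annual eGFR slope. Estimate it with a linear mixed model on all dated eGFR values, with time in years from the first finerenone dose and a random intercept and slope. If a non-user group is formed, give it a comparable time zero and add a group-by-time term.

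If the paired test is kept:
- take the last value before finerenone start as the before value;
- prespecify one later time with a window (12 months is one option, not a figure from the documents);
- state a data cut-off and define eligibility for this analysis by calendar start date relative to it, not by whether a later value exists;
- report the distribution of intervals and the mean change with its confidence interval;
- state that non-significance will not be read as stability.

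The cost is moderate to small: revised wording in sections IV (B) and V, a standard model, and inclusion of serial dated eGFR values in the record export planned in section IV (D). Section VI requires ethics committee approval before protocol changes are implemented. Recent starters contribute little information on slope, and a calendar rule shrinks the paired analysis: with decline 4 and SD 6, power at 12 months is 99% with 43 patients but 81% if only 20 qualify.

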Non-diabetic Chronic Kidney Disease (CKD) poses a significant clinical challenge, with existing treatment methods having limitations [15]. Available approaches are primarily focused on managing the underlying causes of CKD, such as hypertension and proteinuria, to slow disease progression and prevent complications [16]. Common interventions include lifestyle changes, blood pressure control with Angiotensin-Converting Enzyme inhibitors (ACE inhibitors) or Angiotensin Receptor Blockers (ARBs), and the use of Sodium-Glucose Co-Transporter-2 inhibitors (SGLT2 inhibitors) in certain circumstances [17]. However, for CKD without diabetes mellitus (DM), there remains a vital need for novel treatment options for various reasons [1]. New therapies like finerenone show the potential for such advances. Finerenone is a non-steroidal mineralocorticoid receptor antagonist that has been shown to have benefits in studies on patients with CKD and type 2 diabetes, slowing CKD progression and providing cardiovascular protection [18]. Researchers and clinicians are hopeful that this treatment can also be successfully applied to non-diabetic CKD populations, hence there is interest in further research into its efficacy and safety in this particular group [19].

While current non-diabetic CKD treatment strategies include managing hypertension and proteinuria, there is a clear need for new treatment options [20]. Innovative therapies like finerenone that target specific mechanisms of CKD pathology have the potential to improve outcomes and meet the unmet needs of patients with CKD [21]. Further research and clinical trials

are necessary to explore and validate the efficacy and safety of these new therapeutic approaches [22].

Finerenone holds promise for diabetic CKD; however, the lack of evidence for its use in non-diabetic CKD underlines the importance of further clinical research in this area [23]. Such studies would be incredibly valuable for expanding treatment options and improving outcomes for a broader CKD patient population [24].

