Kidney-related indicators and cardiovascular events: including eGFR, serum creatinine levels, records of kidney disease events (such as renal function decline, initiation of dialysis, or kidney transplantation), and records of cardiovascular events.

Safety data: including all adverse events recorded.

(D) Data Collection and Data Management

Determine data sources:

The data will primarily be sourced from the hospital's electronic health record HIS system, which may include clinical records, medication administration records, laboratory test results, and radiological reports.

Acquisition of patient information:

Based on the study's inclusion and exclusion criteria, construct a query to compile a list of patients from the hospital database who meet the criteria for CKD.

Creation of data collection forms:

Create a standardized data collection form listing all the information that needs to be gathered.

Ensure the form includes all the key variable items involved in the study.

Data extraction:

Use the search and export functions of the EHR system to export the required data points for each patient involved in the study. This includes the patient's basic information, medication usage, laboratory test results, etc. For information that cannot be collected automatically, such as physicians' notes or qualitative descriptions in radiological reports, manually extract or enter these into the data tables.

Data entry and coding:

Enter the extracted data into the data collection forms. To protect patient privacy, encode patient information wherever possible to anonymize patient identity within the dataset. For qualitative data, such as diagnoses or symptom descriptions, develop a standardized coding system that converts them into quantitative data suitable for statistical analysis.

Quality control:

Perform data cleaning on the preliminary collected data, checking for missing data, outliers, and inconsistencies. Conduct data verification to ensure the accuracy and completeness of all data. If possible, have two research assistants perform data extraction and entry independently and reconcile any discrepancies.

Data storage and security:

Ensure that all electronic data is stored on secure, password-protected servers or cloud services. Regularly back up data to mitigate the risk of data loss.

Ethical compliance:

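### The before/after renal test has no reference decline and cannot show protection; the controlled renal analysis that could is only optional and is left undefined

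*Combined protocol and SAP*

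**What the plan says.** The last Background paragraph, before Section II, says the design aims to "determine whether the renal protective benefits of finerenone also apply to non-diabetic CKD patients". The same Background states that "CKD is characterized by a gradual and irreversible decline in kidney function over time" and describes the drug's benefit in diabetic CKD as "slowing CKD progression and providing cardiovascular protection".

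The formal wording is milder. Section II speaks of assessing progression following finerenone use. Section III lists "Investigate the changes in renal function in non-diabetic CKD patients after the administration of finerenone" and, separately, "Analyze the relationship between the use of finerenone and cardiovascular events".

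Section V, Hypothesis testing, opens with a condition (if the study aims to compare renal function) and continues "before and after treatment with finerenone, hypothesis testing might be conducted using parametric or nonparametric methods such as paired sample t-tests", with Wilcoxon signed-rank as the alternative. It gives no expected or pre-treatment rate of decline.

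Section V, Survival analysis, is also conditional. It offers Kaplan-Meier curves, log-rank tests between treatment and control groups with CKD progression as the example, and a Cox model of treatment and outcomes adjusted for confounders.

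Section IV (B) sets baseline at the occasion when the patient "was first admitted to the nephrology department for hospital treatment or an outpatient visit". Section IV (D) says to "construct a query to compile a list of patients from the hospital database who meet the criteria for CKD". Neither that query nor the inclusion criteria require finerenone use.

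**The concern.** In a disease that declines without treatment, protection means declining less than would otherwise have happened. A test of change against zero asks something else: whether kidney function moved at all. A working drug can show significant worsening and a useless one can show no significant change. If such a result is published as evidence for or against renal protection, the conclusion is unsupported either way.

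The analysis that could answer the question is in the plan, but it depends on choices that the plan leaves open. Those choices would be made after the data have been seen: Section VIII reports that 43 cases are already organized and show significant differences, without naming the comparison.

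**Working it through.** **No plan figure to reproduce.** The document gives no sample size, power, SD, decline rate, follow-up length or significance level. The calculation below is an illustration.

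**Inputs.** n = 43 (Section VIII, used only as a sample size; the plan does not say whether all 43 are users). Assumed: two-sided 5%; SD of eGFR change 6 ml/min/1.73m² (range 5 to 8); untreated decline D per year; drug slows decline by a fraction f; follow-up T years.

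**Formula.** Mean change m = -D × (1 - f) × T. The paired t statistic is noncentral t with 42 degrees of freedom and noncentrality m√43/SD; the critical value is 2.018.

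**Step 1: same result, different truths (one year).**
- Useless drug, D = 2: m = -2 × 1 = -2.
- Halving drug, D = 4: m = -4 × 0.5 = -2.
- Noncentrality in both: -2 × 6.557/6 = -2.19. Probability of significant worsening in both: 57% (73% at SD 5, 36% at SD 8).

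The equality holds at any SD, provided the SD is the same in both cases.

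**Step 2: same cohort, different drugs (D = 3).** Ranges are over SD 5 to 8.

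| Follow-up | Drug | m | Significant worsening |
|---|---|---|---|
| 1 year | useless | -3 | 89% (67–97%) |
| 1 year | halves decline | -1.5 | 36% (22–48%) |
| 4 months | useless | -1 | 19% (12–25%) |
| 4 months | halves decline | -0.5 | 8% (6–9%) |

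The halving drug shows significant improvement at one year in only 0.02% (0.005–0.08%). A drug that stops decline altogether (m = 0) rejects at the 5% error rate, 2.5% in each direction. The Wilcoxon test behaves alike: by simulation at SD 6, 0.880 for m = -3 and 0.345 for m = -1.5.

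**Step 3: only if first contact is the 'before' value.** Suppose a share p of baselines is depressed by 10 units and recovers, and the drug is useless with D = 3. Mean change is then m + 10p. Simulated at SD 6:
- One year (m = -3): significant worsening falls from 89% to 48%, 15% or 3% at p = 10%, 20% or 30%.
- Four months (m = -1): false significant improvement in 2%, 13% or 39% at the same shares.

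The 3% is a special case: 10 × 0.30 = 3 exactly cancels the assumed decline of 3.

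**Step 4: what the controlled option leaves undefined.** No section says who the controls are, when their clock starts, what counts as a kidney event, which covariates enter, or which analysis is primary. The only defined baseline is first nephrology contact, not finerenone start.

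**The case against.** The strongest reply is that the plan already contains a controlled renal analysis. The survival paragraph ties treatment-versus-control log-rank tests to CKD progression and adds a confounder-adjusted Cox model, and Section IV (C) collects renal decline, dialysis and transplantation. This stands. A reader might infer that no controlled renal comparison is foreseen, or that the plan can never show protection; the document supports neither. The group comparisons and logistic regression in Section V could also be applied to users and non-users, since CKD stage and cardiovascular events appear there only as examples. But naming a test is not specifying a contrast, and all of these are options.

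Second, the Section II objective and the renal item in Section III are descriptive, and a before/after summary suits them. This also stands, and it is why a descriptive fallback is acceptable. It does not cover the Background's aim about protection.

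Third, every magnitude except n = 43 rests on assumptions. That is true, but the equivalence in Step 1 is algebraic and does not depend on the chosen SD.

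Fourth, a between-group contrast at this size has low power. That is correct, and is a reason to report an estimate with its interval. It is not a reason to rely on a test that addresses a different question.

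**Conclusion.** The point holds in this form: the before/after test cannot support a conclusion about renal protection in either direction, and the controlled analysis that could is optional and undefined. In the illustration, a useless and a working drug share a 57% chance of significant worsening (36–73% over SD 5 to 8).

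Three further readings go beyond the document. It does not say that first contact is the 'before' value, so the rebound figures are conditional. It does not say that the preliminary significant differences came from a paired test. It does not restrict the cohort to users, so non-users may be available; how many there are is not stated.

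**What to change.** 1. State that the paired test is descriptive and that no conclusion about protection is drawn from it.
2. Make finerenone users versus non-users the main renal contrast. Draw non-users from the same CKD query. Set time zero at finerenone start for users and at a matched index date for non-users.
3. Compare eGFR slopes from all dated values in a linear mixed model adjusted for baseline eGFR and recorded confounders, and report the estimate with its interval. Report whether each index value came from an admission or an outpatient visit, because moving time zero does not remove rebound if treatment starts during an acute dip. Complete the named log-rank/Cox analysis with listed covariates and a defined kidney event that includes dialysis and transplantation, since these can truncate slopes.
4. If too few non-users exist, limit the conclusion to a description of change.

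**Cost.** SAP wording, group and index-date definitions, and extraction of dated eGFR values. Intervals widen. For a simple comparison of one-year change (SD 6; range for SD 5 to 8), the 95% half-widths are:
- single group: 2.018 × 6/√43 = 1.8 (1.5–2.5);
- 43 per group: 1.989 × 6 × √(2/43) = 2.6 (2.1–3.4);
- 43 users and 129 non-users: 2.1 (1.7–2.8).

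Power for a 1.5-unit difference is 21% (14–28%) at 43 per group and 29% (18.5–39.5%) with 129 non-users. Residual confounding remains, and if the share of depressed baselines differs between groups by 10 percentage points, the bias is 10 × 0.10 = 1 unit. Step 1 with the step 4 fallback costs only wording.
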